4.2 Intervention

All study participants will receive 10mcg 17-β estradiol tablets. At the initial medicine or gynecology visit, we will instruct each patient to insert one 10mcg 17-β estradiol tablet into her vagina at bedtime for two weeks as the initiation dose. After the initial two-week period ends, the dosing will decrease to one tablet vaginally two times per week for the subsequent 22 weeks for maintenance. A member of the clinical research staff will explain the proper method of treatment administration using a standardized script. Patients can also refer to the package insert during the initial visit for further clarification. Patients will also be asked to keep a medication diary. In it they will record the date and time each estrogen tablet is used. They will also record any symptoms or side effects they experience. They will be required to bring completed diaries to their appointments.

Timepoints for FSH and estradiol bloodwork and FSFI survey:

Weeks	FSH	Estradiol	FSFI/Menopause Symptom Checklist
0	X	X	X
2	X	X	
7	X	X	
12	X	X	X
18	X	X	
24	X	X	X

5.0 THERAPEUTIC/DIAGNOSTIC AGENTS

Vaginal 17- β estradiol is an FDA approved medication for the treatment of atrophic vaginitis. Each 17- β estradiol vaginal tablet contains 10 micrograms of estradiol. Vaginal administration circumvents first pass metabolism that occurs with oral estrogens, and the levels of estradiol and estrone are within postmenopausal range after a 12 week course of vaginal 17- β estradiol in postmenopausal women who do not have breast cancer.¹⁷

Reported adverse events (%17- β estradiol vaginal vs placebo) in a placebo controlled trial where 91 patients received 17- β estradiol vaginal and 47 patients received placebo included headache (9 vs 6), abdominal pain (7 vs 4), upper respiratory tract infection (5 vs 4), genital moniliasis (5 vs 2) and back pain (7 vs 6).¹⁷ Adverse events (%) reported in an open label study of 80 patients included genital pruritus (6), headache (10), and upper respiratory tract infection (11). Other adverse events that occurred in less than 5% of patients included allergy, bronchitis, dyspepsia, hematuria, hot flashes, insomnia, pain, sinusitis, vaginal discomfort, and vaginitis although a causal relationship to 17- β estradiol has not been established.

6.0 CRITERIA FOR SUBJECT ELIGIBILITY

The following eligibility criteria will be used:

6.1 Subject Inclusion Criteria

- History of breast cancer, stages I-III with pathology confirmed at MSKCC
- Women who have completed all of their primary treatment (surgery, radiation therapy, adjuvant chemotherapy) with the exception of endocrine therapy and currently have no clinical evidence of disease.
- Women who are currently on aromatase inhibitors for at least three months--either letrozole or anastrozole

- Women with symptomatic urogenital atrophy: vaginal dryness, irritation, pruritus, dyspareunia, urinary frequency and/or urinary incontinence
- Menopausal at study entry defined as:
 - Bilateral salpingo-oophorectomy independent of age
 - If natural menopause, age ≥ 50 with cessation of menses for at least 12 months
 - If menopause induced by chemotherapy, age ≥ 50 with no menstrual period at least 12 months after chemotherapy finished
- At least 18 years of age
- Able to participate in the informed consent process
- Gynecology examination within six months
- Able to read/speak English.

6.2 Subject Exclusion Criteria

- Inability to give informed consent
- Vaginal bleeding of unknown etiology within 12 months of study entry
- History of prior vaginal 17- β estradiol or other topical estrogen use within the past six months

7.0 RECRUITMENT PLAN

Women at breast medicine oncology clinics and gynecology clinics at Memorial Sloan-Kettering Cancer Center (MSKCC) will be identified by their treating physicians as potential research subjects. If the investigator is a member of the treatment team, s/he will discuss the study with the patient. Otherwise the patient will be referred to an investigator.

During the initial conversation between the investigator/research staff and the patient; the patient may be asked to provide certain health information that is necessary to the recruitment and enrollment process. Specifically, patients will be asked about symptoms related to urogenital atrophy. The investigator/research staff may also review portions of her medical records at MSKCC in order to further assess eligibility. They will use the information provided by the patient and/or medical record to confirm that the patient is eligible and to contact the patient regarding study enrollment. If the patient turns out to be ineligible for the research study, the research staff will destroy all information collected on the patient during the initial conversation and medical records review, except for any information that must be maintained for screening log purposes. If the woman agrees to study participation, a consenting individual (listed below in section 15.1) will obtain informed consent from the patient until a goal of 60 eligible patients are entered into the study in order to have 48 evaluable patients.¹⁸

In most cases, the initial contact with the prospective subject will be conducted either by the treatment team, investigator or the research staff working in consultation with the treatment team. The recruitment process outlined presents no more than minimal risk to the privacy of the patients who are screened and minimal PHI will be maintained as part of a screening log. For these reasons, we seek a (*partial*) limited waiver of authorization for the purposes of (1) reviewing medical records to identify potential research subjects and obtain information

relevant to the enrollment process; (2) conversing with patients regarding possible enrollment; (3) handling of PHI contained within those records and provided by the potential subjects; and (4) maintaining information in a screening log of patients approached (if applicable).

8.0 PRETREATMENT EVALUATION

After informed consent is established, subjects will have a blood sample drawn for a baseline estradiol and FSH level and complete a baseline FSFI. Baseline bloodwork and the baseline FSFI will be drawn within 14 days of study enrollment prior to the initiation of vaginal 10 μ g 17- β estradiol. During the initial visit, we will perform a history and physical examination to confirm that the subject has no evidence of disease. A gynecological exam will also be performed if the patient's last examination was more than six months ago.

9.0 TREATMENT/INTERVENTION PLAN

At the initial medicine or gynecology visit, we will instruct patients to insert one estradiol tablet into their vagina at bedtime for two weeks and then one tablet twice weekly for the subsequent twenty-two weeks. Treatment will begin within two weeks of the initial visit after the baseline bloodwork has been drawn and the baseline FSFI/Menopause symptom checklist is completed. A member of the clinical research staff will explain the proper method of treatment administration using a standardized script. Patients can also refer to the package insert for further clarification. We will instruct patients not to use other forms of transvaginal estrogens or vaginal moisturizers while actively participating in the study to avoid biasing of the results. Water based lubricants will be allowed.

10.0 EVALUATION DURING TREATMENT/INTERVENTION

All subjects will receive vaginal 10 μ g 17- β estradiol tablets. Each subject will serve as their own control. Serum estradiol and follicle stimulating hormone (FSH) will be monitored closely from 0-24 weeks. Serum estradiol and FSH levels will be measured at baseline, and subsequently at weeks 2, 7, 12, 18 and week 24 after commencing therapy with vaginal 10 μ g 17- β estradiol. The bloodwork will take less than one hour and will be drawn +/- 72hrs from the date the patient is due for bloodwork. Baseline bloodwork will be drawn within 14 days of study enrollment prior to the initiation of vaginal 10 μ g 17- β estradiol. Patients will be encouraged to come for their research bloodwork 12-24 hours after the insertion of the vaginal 10 μ g 17- β estradiol tablets. Patients will record in their diary the time of their last vaginal 10 μ g 17- β estradiol tablet insertion. Both the patients and the investigators will be blinded to the results of these assays for the 24 weeks of study therapy. Results will be unblinded after accrual is complete and all patients have completed the 24 weeks of planned therapy. At week 24, patients can choose to remain on vaginal 10 μ g 17- β estradiol or discontinue the treatment. Patient's estradiol levels may continue to be monitored for the duration of their treatment with vaginal 10 μ g 17- β estradiol at her physician's discretion and depending on the findings of this study. We will continue to collect this data. Patients can choose to remain on it for as long as they desire.

Patients will complete the FSFI survey and menopause symptom checklist at baseline, week 12 and week 24. The FSFI will take ten minutes to complete and the menopause symptom checklist

will take three minutes to complete. Both will be administered +/- 72hrs from the date the patient is due for the survey. The baseline FSFI/ menopause symptom checklist will be completed within 14 days of study enrollment prior to the initiation of vaginal 10 μ g 17- β estradiol. Patients will also be asked to keep a medication diary. In it they will record the date and time each estrogen tablet is used. They will also record any symptoms or side effects they experience. They will be required to bring completed diaries to their appointments. If a patient discontinues vaginal 10 μ g 17- β estradiol, information will be gathered regarding her reason(s) for discontinuation and this information will be recorded in the medical record. If a patient fails to return for assessment during the defined intervals, she will be contacted by one of the investigators and information will be gathered regarding her reason(s) for not returning. If she is still using vaginal 10 μ g 17- β estradiol, she will be asked to return to have her estradiol level checked.

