2.0 OBJECTIVES AND SCIENTIFIC AIMS

SPECIFIC AIMS:

Primary Specific Aim:

- To determine the change in estradiol and FSH from baseline to twelve weeks in postmenopausal women receiving adjuvant aromatase inhibitors during treatment with low dose vaginal 10 μ g 17- β estradiol.

Secondary Specific Aims:

- To compare the rise in estradiol in women on letrozole vs. anastrozole during treatment with low dose vaginal 10 μ g 17- β estradiol to see if there are differences between aromatase inhibitors.
- To describe patterns of estradiol and FSH levels over the twenty-four week study period.

- To compare the patient's FSI scores and menopause quality of life questionnaire at baseline, week 12 and week 24

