The primary analysis will focus on analyzing the change in estradiol level from baseline to 12 weeks using a two-sided paired t-test. We plan to recruit sixty eligible women, with the expectation that 48 (80%) will complete the study and be compliant. We plan to recruit 30 women who have been on anastrozole therapy and 30 women who have been on letrozole therapy. Patients who drop out due to self-withdrawal, recurrence or noncompliance will be eliminated from the primary analysis but will be examined closely. Patients are evaluable if they have at least baseline and week 12 values.

The primary analysis will be a two-sided paired t-test to evaluate whether there was a change in estradiol levels from baseline to 12 weeks. For a sample size of 48, we will be able to detect a difference of .41 or higher on a standard unit scale with 80% power and **5% type I error** using a paired t-test. To translate this into the scale commonly used to report estradiol, we examine a series of 6 breast cancer patients published by Kendall et al (2006). In Kendall et al, estradiol levels ranged from close to 0 to 5 pmol/l before starting vaginal estradiol, to close to 0 to 25 at 7 weeks. Based on these data, we conservatively estimate the standard deviation of the difference to be 7 (**roughly, range/4**). Thus, for a sample size of 48 we will be able to detect an absolute difference in estradiol of 2.88 pmol/l with 80% power and **5% type I error**.

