In addition to the main analysis described above, there are several secondary analyses planned for the FSH and FSFI/menopause checklist endpoints. Two-sided paired t-tests will be performed to evaluate change in FSH levels from baseline to 12 weeks and FSFI from baseline to 12 weeks and baseline to 24 weeks. To adjust for covariates of interest, such as type of aromatase inhibitor, an ANCOVA will be fit to the data. Trends of estradiol levels, FSH levels, and FSFI/menopause symptoms over the course of the study for all available timepoints will also be examined using graphical methods and repeated measures models. The graphs will illustrate patients and drug-specific short- and long term variations in estradiol (primary endpoint), FSH, and FSFI/menopause symptoms (secondary endpoints). It is hypothesized that estradiol levels will increase until approximately week 12 and then return to baseline after the vaginal walls reepithelialize. It is also hypothesized that FSH will remain constant throughout the 24 weeks and the FSFI/some menopausal symptoms will show improvement from baseline to both 12 and 24 weeks. To bring data from all these timepoints together, we will fit a repeated measures model²⁰ and if needed adjust our model to allow the time-effect to be modeled nonparametrically.²¹ Modeling the time-effect nonparametrically may be needed if estradiol trends over time, for example, do not have a simple parametric form such as a straight line or a quadratic curve. Model parameters and graphs of the raw data will help us identify where there are increases, decreases, or plateaus in estradiol, FSH, and FSFI over the study period. All these models can be fit in standard statistical software like SAS for Windows.

As in any prospective study, we expect missing data on a subject and item level. This is a small study, and thus, we do not plan to do any imputation. However, we will evaluate the degree of missingness in the final study by calculating attrition rates and the percent of missing values for a given variable. We will also examine the patient characteristics of the patients who have missing values. All analyses will be interpreted with missing data issues in mind.

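### The recall rule omits women who have stopped the tablets, so week-12 and week-24 FSFI scores may be lost selectively and the reported change may favour women who continue

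*Combined protocol and SAP*

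**What the plan says.** All references are to the combined protocol and SAP.

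- **Stopping the tablets.** Section 10.0: "information will be gathered regarding her reason(s) for discontinuation and this information will be recorded in the medical record". Section 4.1 says much the same. Neither says whether the questionnaires continue.
- **Missing a visit.** Section 10.0: "If a patient fails to return for assessment during the defined intervals, she will be contacted by one of the investigators", and her reasons are asked. The next step is conditional: "If she is still using vaginal 10 μ g 17- β estradiol, she will be asked to return to have her estradiol level checked". Section 4.1 has the same condition.
- **FSFI schedule.** Section 10.0: "Patients will complete the FSFI survey and menopause symptom checklist at baseline, week 12 and week 24". This carries no on-treatment condition. Section 2.0 lists the matching secondary aim: "To compare the patient's FSI scores and menopause quality of life questionnaire at baseline, week 12 and week 24" (FSI there is the FSFI).
- **Removal from study.** Section 13.0 gives three grounds: recurrent or progressive disease, related toxicity of grade 3 or higher, and ineligibility. Stopping the tablets is not one of them.
- **How questionnaires are given.** Sections 4.1 and 16.0 describe paper or tablet computers in clinic waiting rooms, brought by the study assistant at visit dates.
- **Analysis.** Section 14.0 plans paired t-tests of FSFI from baseline to week 12 and from baseline to week 24, plus repeated measures models on all available time points. On missing data: "This is a small study, and thus, we do not plan to do any imputation". Attrition, percent missing and the characteristics of women with missing values will be reported.
- **Expected loss.** Sixty women are recruited "with the expectation that 48 (80%) will complete the study and be compliant". The rule that drops withdrawals, recurrences and noncompliers is written for the primary (estradiol) analysis. No FSFI analysis set is defined.

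**The concern.** Recalling only current users suits a question about estradiol levels on treatment. It suits a symptom score less well, because poor relief is both a reason to stop and the thing being measured. Women also pay for the tablets themselves (section 17.0), which is a further plausible reason for someone without benefit to stop.

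A woman who has stopped and no longer attends remains on study under section 13.0. Yet she is not asked back, and the only described route to the questionnaire is a clinic visit. She then has no follow-up score and falls out of the paired tests.

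Section 14.0 predicts FSFI improvement at both time points, and there is no control group. Within-woman change is therefore the only information the study will have on symptom benefit. If the missing scores come mainly from women who did less well, that change will look better than it was among all women treated.

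**Working it through.** **1. The plan's own figures.** Inputs from section 14.0: 60 recruited, 48 expected to complete and comply, two-sided 5% error, 80% power.
- 48/60 = 80%, and 48/0.80 = 60, as stated.
- Paired t-test with n = 48 (noncentral t, 47 degrees of freedom): detectable difference 0.413 SD against the stated 0.41. At the plan's SD of 7 this is 2.89 pmol/l against 2.88. Both reproduce.
- These figures concern estradiol. The documents give no effect size, SD or loss by reason for the FSFI, so steps 3 to 5 use assumed ranges.

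**2. Who can be missing.** At the planned loss, at most 60 − 48 = 12 women lack a follow-up FSFI. The 12 include recurrences, withdrawals and noncompliers, and a noncomplier may still attend and give a score.

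**3. Size of the selection effect.** Let C be the mean change in women with both scores, d the share without a follow-up score, and rC the mean change in the missing women.

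All-enrolled mean = (1 − d)C + d·rC. Overstatement = 1/(1 − d + d·r) − 1.

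With d = 0.20:

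| r (assumed) | All-enrolled mean | Overstatement by completers |
|---|---|---|
| 1 (same as completers) | 1.00C | 0% |
| 0.5 | 0.90C | 11% |
| 0 (no change) | 0.80C | 25% |
| −0.5 | 0.70C | 43% |
| −1 (worsen equally) | 0.60C | 67% |

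With r = 0, the overstatement is 1/0.9 − 1 = 11% at d = 10% and 1/0.7 − 1 = 43% at d = 30%.

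The sign can reverse. If women stop because symptoms resolved and r = 1.5, the all-enrolled mean is 0.8C + 0.3C = 1.10C, and completers understate it by 1 − 1/1.10 = 9%.

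**4. How far it could go.** For the all-enrolled mean to be zero at d = 0.20, 0.8 + 0.2r = 0 gives r = −4. The missing women would have to worsen by four times the completers' gain.

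**5. Effect on the test.** Suppose the true all-enrolled change is zero and missing women do g SD worse than completers. Then 0.8C + 0.2(C − g) = 0, so C = 0.2g. With n = 48, the two-sided rejection rate is 6.3% for g = 0.25, 10.4% for g = 0.5 and 27.4% for g = 1, against a nominal 5%.

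**6. What the repeated measures model recovers.** The FSFI has two follow-up times. A woman with a week-12 score but no week-24 score stays in the model. A woman with a baseline score alone contributes no observed change. For both, the estimate is sound only if missingness depends on what was observed, which is doubtful if she left for lack of relief.

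**The case against.** The strongest reply is that the plan is silent on FSFI after stopping and does not exclude these women. The schedule covers all patients, stopping is not a ground for removal, and the exclusion rule names only the primary analysis. A woman who stops but still attends can complete the FSFI and be counted. This stands. A reader might infer that the FSFI is analysed without women who stop, or that it describes only women content to continue; the documents support neither, and a dissatisfied woman may also continue.

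Second, the plan has safeguards: the repeated measures model on all available time points, reporting of attrition and of who is missing, and collection of reasons for stopping and for not returning. These also stand, and they mean the paired tests are not the only FSFI analysis. But describing a gap does not fill it, and the model cannot supply change for women with a baseline score alone.

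Third, the quoted recall rule concerns estradiol, so the FSFI consequence is inferred. True. The inference rests on that rule being the only one for non-attenders and on in-clinic administration being the only route described.

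Fourth, a reader might infer that improvement is overstated by a definite amount, or that the bias grows from week 12 to week 24 and mimics continuing benefit. The documents give no FSFI change for any group and do not split the expected loss by week, so neither can be claimed.

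Finally, the FSFI is a secondary endpoint of an uncontrolled pilot. Complete follow-up would not turn a before-after change into proof of efficacy. That limits the weight of the point, but the fix is still worth its small cost.

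**Conclusion.** The concern holds in limited form. Followed as written, the plan does not seek FSFI scores from women who have stopped and no longer attend, and its paired tests use complete pairs without a sensitivity analysis. The reported FSFI change may therefore be selected toward continuers. Upward is the more probable direction, but it is not demonstrated.

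The overstatement runs from 0% to 67% over the assumed range from equal change to equal worsening, with 25% if the missing women do not change. This takes the planned 20% loss and treats all 12 women as missing, which is the upper bound at that loss. A complete reversal of the finding would need an extreme assumption. This is a low-cost improvement to a secondary endpoint and does not affect the primary estradiol analysis.

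**What to change.** **Sections 4.1 and 10.0.** State that every woman who stops the tablets, but has not withdrawn consent or been removed from study, is asked to complete the FSFI and symptom checklist at weeks 12 and 24. Apply this to missed visits as well.

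**Section 14.0.** Define the FSFI analysis set as all women with a baseline score. Make the repeated measures model already planned the main FSFI analysis and show the paired t-tests beside it. Add a sensitivity analysis that assumes no change from baseline in non-returners. Leave the estradiol analysis set unchanged.

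**Cost.** Wording changes, some extra contact effort, and about 10 + 3 = 13 minutes of questionnaires per affected woman per time point. An online survey platform exists, but only in-clinic administration is described, so remote completion would need to be confirmed. Women who withdraw or are removed will still be missing. The reported FSFI gain may turn out smaller. Scores not collected at the time cannot be recovered later.

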11.0 TOXICITIES/SIDE EFFECTS

Because serum estrogen levels with low dose vaginal 17 β -estradiol are within postmenopausal range, the potential risks associated with systemic estrogen use are not expected to occur.¹⁹ A recent double-blind, randomized study of vaginal 25 μ g 17 β -estradiol vs 10 μ g 17 β -estradiol in postmenopausal women shows that after 12 weeks of therapy for atrophic vaginitis, women did not have accumulations of circulating estradiol.⁴

As previously stated (see section 5.0), adverse events reported with 17 β -estradiol vaginal vs placebo in a controlled trial included headache (9% vs 6%), abdominal pain (7% vs 4%), upper respiratory tract infection (5% vs 4%), genital moniliasis (5% vs 2%), and back pain (7% vs 6%).¹⁷ In an open label study of 80 patients, adverse events included genital pruritus (6%), headache (10%), and upper respiratory tract infection (11%). Other adverse events that occurred in less than 5% of patients included allergy, bronchitis, dyspepsia, hematuria, hot flashes, insomnia, pain, sinusitis, vaginal discomfort, and vaginitis, although causal relationships cannot be established.

The benefits include the advancement of knowledge relating to the treatment of urogenital symptoms in the breast cancer patient with possible benefit for both current and future patients.

